### **Participant Recruitment, Screening, and Enrollment:**

#### Main study:

We will enroll up to 80 women, with a goal of 40 to complete the substudy Part A phase 2 or Part B. We will post flyers in the WIC office regarding the study opportunity and WIC staff will wear tags about the study (optional for WIC staff to wear)— see Appendix Q and R.

The UCD PRA will review the WIC records for upcoming appointments for each day and pre-identify those women who are 3-12 months postpartum. She will share the list of those with appointments meeting this criteria with the WIC staff, reminding them to introduce the study opportunity to the person at the end of the appointment.

WIC staff will introduce the study to postpartum women at the end of a visit to WIC. Before introducing the study to a person, the WIC staff person will screen for 3 eligibility criteria using data available to her. 1) Person is 3-12 months postpartum, 2) WIC is not recommending to come back to WIC prior to 3 months, and 3) if data is available, person meets current BMI eligibility. If the person meets these criteria, the WIC staff member will introduce the study to the person. They will also give them the flyer (Appendix C) with more information about the study and the screening questions for the person to review (Appendix A.2 page 1 only). This screening done by the WIC staff member ensures that the study is not offered to women who are not eligible based on data already available at WIC.

We will recognize WIC staff efforts to present the study to WIC clients meeting the above criteria by giving \$5 gift cards. These gift cards will be given on about a weekly basis to WIC staff demonstrating active engagement in supporting the study. This includes, but is not limited to those presenting the study the most frequently to WIC clients, having a positive attitude about the study, or encouraging other WIC staff to help recruit for the study.

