the RA will meet 1 on 1 to address any further questions the person may have about the study. The RA will then read the consent form to the person, who will have their own copy to read along. The consent contains information about the study procedures and risks. It also recommends that participants should check with their medical provider before starting to exercise. We will NOT require individuals to bring in a note from their medical provider. The RA will answer any questions as needed. For those ready, the RA will complete the informed consent process and enroll the person in the study. As part of the consent process, participants will be offered to take additional time if needed to decide. If they need additional time, they will be asked to call the RA if they decide they are interested in participating. If this happens, they will be asked to come meet in person with the RA at the WIC office to complete the informed consent process and enroll in the study. We will stress during this informed consent process that participation in our research study is voluntary, that subjects may withdraw from the study at any time, and that the investigators reserve the right to discontinue the research protocol at any time. A copy of the signed informed consent form will be given to each subject. Appendix E is the main study consent form.

The Aurora WIC sees over 700 women monthly. Over 50% of these women report being overweight or obese pre-pregnancy. Given these high numbers and the importance of this topic to women in WIC (as described by WIC clients during prior stakeholder meetings), we expect to complete enrollment within a 2-4 month time period.

Treatment assignment: Following informed consent, women will be randomly assigned to the lifestyle group (intervention) or observation group (control). We will use a computer program to randomize subjects using block randomization, to ensure equal numbers of intervention and control participants, given the small sample size. We will randomize in blocks of 10 using a random number generator where 1= intervention (Lifestyle group) and 2= control (Observation group). The RA will have sealed envelopes labeled and ordered from 1 up. The RA will open the next envelope in order of consenting to assign the participant to the intervention or control arm.

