Confidentiality: The Principal Investigator and her staff will take all reasonable measures to protect the confidentiality of each subject's records and data. Subject data will be referenced by number only. Research data on paper will be kept in a secured file cabinet in a secured office area. Research data kept online will be kept secure and confidential through password protection. Data will be stored in RedCap. Audiorecordings will be stored on a secure University server. Data kept on HeartSmartMoms will have participant ID number, but no other identifiable information.

**E. Potential Scientific Problems:** This is a pilot intervention that has never been trialed before. It is based on information gathered from WIC staff, WIC leadership, WIC clients and is based on evidence from other settings. However, because it has never been trialed before, we may find significant feasibility and acceptability issues leading to significant attrition, making it impossible to complete Aim 2 for the main and substudies. Given that this is a feasibility trial, with a small sample

size, we may also not have enough power to detect differences between intervention and control participants if the differences are small.

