## **F. Data Analysis Plan:**

Aim 1: To evaluate the feasibility and acceptability of a multi-component novel weight loss intervention delivered in a WIC setting to a population of low-income, predominantly racial/ethnic minority, obese, postpartum women.

- The RA will transcribe the audiorecorded responses to open-ended questions posed to participants and WIC staff on acceptability. We will use a thematic analytic approach to analyze the data. After reading and discussing all responses amongst team members, we will create a list of codes. We will then use an iterative process to revise codes as needed and identify main themes. We will use a software program (Atlas.ti) for coding. We will assess the ease of recruiting women for the study (number enrolled/number approached) and attrition from the study. We will also calculate the intervention adherence measures, including number of women who received the entire intervention, number of women who came to all visits, participation in self-monitoring, use of phone coaching, and use of the Facebook page. For the Facebook page, we will count the number of posts/individual and categorize the content based on the type of content we see.

Aim 2: To evaluate differences in diet, physical activity, self-efficacy, eating stimulus, and weight change between intervention and control participants to determine preliminary intervention efficacy over a 12-week period.

- We will conduct a univariate analysis of variables to evaluate for baseline group differences, distributions, and outliers for demographic, lifestyle and infant feeding variables. Student t-tests will be used to test for differences between intervention and control groups in change in weight (baseline to 12 wks) and in lifestyle habits using a 2-tailed  $\alpha=0.05$  for statistical significance. [name] will conduct the analysis in consultation with the Child Health Research Biostatistical Core.

Sample Size: This is a feasibility trial, hence, we will not be powered to detect all clinically significant findings. The sample size was chosen based on the sample needed to achieve Aim1. The sample size is 40 (20 intervention and 20 control). We are asking for a sample size in the application up to 80 in case we have a large number of individuals enroll but not participate in the substudy. Given that this is a feasibility trial, we are unsure how difficult recruitment will be.

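### The Aim 2 comparisons should name the Welch t-test: the equal-variance Student test drifts from 5% if the arms end with both unequal numbers and unequal spread

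*Combined protocol and SAP*

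**What the plan says.** Section IV.F (Data Analysis Plan, Aim 2) gives one between-arm method: "Student t-tests will be used to test for differences between intervention and control groups in change in weight (baseline to 12 wks"), and also "in lifestyle habits using a 2-tailed" level of 0.05. It names no unequal-variance version, variance check, confidence interval or rule for missing 12-week data.

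On numbers, the same section says "The sample size is 40 (20 intervention and 20 control"), and concedes that "we will not be powered to detect all clinically significant findings". The recruitment section allows more: "We will enroll up to 80 women, with a goal of 40 to complete the substudy Part A phase 2 or Part B". Allocation is 1:1 in blocks of 10: "We will use a computer program to randomize subjects using block randomization, to ensure equal numbers of intervention and control participants".

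On loss, section IV.E warns that "we may find significant feasibility and acceptability issues leading to significant attrition". It gives no rate and does not say that one arm would lose more. No SD of weight change is given for either arm anywhere.

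**The concern.** The Student t-test in its conventional form pools the two sample variances. With equal arms this does little harm even when the SDs differ. With unequal arms the pooled variance is weighted towards the larger arm. If the smaller arm is the more variable one, the standard error is too small and the test rejects too often; in the reverse case it is too large and the test rejects too seldom.

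Blocking secures equal numbers at randomisation, not at week 12, and the design contains reasons why the analysed numbers could part:

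- Lifestyle women have extra visits at 4 and 8 weeks and receive WIC benefits in 4-week amounts, which section IV.D accepts may add burden.
- Lifestyle women learn of the second substudy phase and its payment only at the 12-week visit. Observation women are offered both survey time points at baseline and receive their gift card at week 12.
- For the lifestyle outcomes, consent to the substudy also runs differently by arm.

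Spread could differ too. Phone coaching is on request, counselling is tailored, and use of texts and Facebook will vary, so a programme that works may work unevenly.

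At stake are the p-values, and any interval built on the pooled SD, for results that section IV.G says will inform whether to evaluate the intervention on a larger scale and how large later studies should be.

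**Working it through.** **Inputs from the documents.** Student t-test, two-sided 0.05, 20 per arm, 1:1 allocation, enrolment ceiling 80 (all from section IV.F and the recruitment section).

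**Assumed, because the documents are silent.** Ratio *r* of the larger to the smaller SD: 1 to 2. Loss confined to one arm: 30% (6 of 20, leaving 14 v 20) or 40% (8 of 20, leaving 12 v 20). Changes are taken as normal.

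**Formulas.** Let arm 1 have SD *r* and arm 2 have SD 1.

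- True variance of the mean difference: V = r²/n₁ + 1/n₂.
- Variance that the pooled test estimates, on average: V_P = {[(n₁−1)r² + (n₂−1)] / (n₁+n₂−2)} × (1/n₁ + 1/n₂).
- Actual two-sided error: the mean of 2Φ(−c√(S_p²(1/n₁+1/n₂)/V)) over the two independent chi-square sample variances, where c is the 97.5% point of t with n₁+n₂−2 degrees of freedom. For normal data this does not depend on the true mean difference, so it is also the miscoverage of a pooled 95% interval.

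**The plan's own figure.** At 20 v 20 with equal SDs the actual error is 5.0%, so the stated level is reproduced.

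**Moderate case, 14 v 20, r = 1.5.**

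- Smaller arm more variable: V = 2.25/14 + 1/20 = 0.2107. V_P = [(13×2.25 + 19)/32] × (1/14 + 1/20) = 1.508 × 0.1214 = 0.1831. The pooled standard error is √(0.1831/0.2107) = 0.93 of the true one. Actual error 6.8%.
- Larger arm more variable: V = 2.25/20 + 1/14 = 0.1839. V_P = [(19×2.25 + 13)/32] × 0.1214 = 0.2116. Ratio of standard errors 1.07. Actual error 3.7%.

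**Strong case, 12 v 20, r = 2.**

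- Smaller arm more variable: V = 4/12 + 1/20 = 0.3833. V_P = [(11×4 + 19)/30] × (1/12 + 1/20) = 2.1 × 0.1333 = 0.2800. Ratio 0.85. Actual error 9.6%.
- Larger arm more variable: V = 4/20 + 1/12 = 0.2833. V_P = 2.9 × 0.1333 = 0.3867. Ratio 1.17. Actual error 2.5%.

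| Analysed numbers | SD ratio | Pooled, smaller arm more variable | Pooled, larger arm more variable |
|---|---|---|---|
| 20 v 20 | 1 | 5.0% | 5.0% |
| 20 v 20 | 1.5 | 5.1% | 5.1% |
| 20 v 20 | 2 | 5.2% | 5.2% |
| 14 v 20 | 1 | 5.0% | 5.0% |
| 14 v 20 | 1.2 | 5.8% | 4.4% |
| 14 v 20 | 1.5 | 6.8% | 3.7% |
| 12 v 20 | 1.2 | 6.1% | 4.1% |
| 12 v 20 | 2 | 9.6% | 2.5% |

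(In the 20 v 20 rows the arms are equal, so the two columns coincide.)

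Enrolling up to the ceiling does not help: 24 v 40 at r = 2 gives 9.4%, and the reverse gives 2.4%. What matters is the proportional loss. Simulation with 200,000 trials agrees (12 v 20 at r = 2: 9.5%; reverse: 2.5%).

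**Welch.** Across 8 to 40 per arm and SD ratios 1 to 3, its actual error is 4.9% to 5.2%. Its power cost when the SDs are equal, for an assumed difference of 0.9 SD, is 79.1% to 79.0% at 20 v 20 and 66.6% to 65.5% at 12 v 20.

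**The case against.** The strongest case against is that both conditions are undocumented and must hold together. Attrition is described as something that may happen, not something expected. No arm is singled out, and both arms get the same reminders and rescheduling. No SD is given. With equal arms, or with equal SDs, the level stays at about 5%. This stands, and it is why the figures are conditional.

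A second objection concerns the null hypothesis. If the intervention does nothing for anyone, uneven uptake adds no spread, the randomised arms share one variance, and without selective loss the pooled test keeps 5% at any split. A false-positive excess needs individual effects that average to zero. If these are independent of background change, their SD must be √(1.5²−1) = 1.1 times the control SD for a ratio of 1.5, and √(2²−1) = 1.7 times for a ratio of 2. This stands for the p-value under a wholly inert intervention. It does not dispose of the point: when the intervention works unevenly, a pooled interval misses the true difference at the rates tabulated above. The plan names no interval, but a pooled one is the natural companion of a Student test.

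Third, the text does not use the words pooled or equal variance, and the analysis is to be done in consultation with a biostatistical core, which might choose Welch anyway. That is fair, but it argues for saying so in advance rather than choosing after the data are seen.

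Lastly, weight change is a secondary outcome of a feasibility pilot whose limited power is acknowledged. This stands and limits the importance of the point.

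**Conclusion.** The point holds as a minor one. As written, the plan's test is exposed to an error rate that can move in either direction if unequal numbers and unequal spread coincide: about 4.4% to 5.8% at 14 v 20 with SD ratio 1.2, about 3.7% to 6.8% with SD ratio 1.5, and about 2.5% to 9.6% in the strong case of 12 v 20 with SD ratio 2. The splits and SD ratios are assumptions. Unequal analysed numbers are plausible from the design; unequal spread is an inference from varying uptake.

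A reader might infer that the true error is likely to be about half or double the stated 5%. The documents do not support that. It takes some 40% loss confined to one arm together with a two-fold SD ratio (a four-fold variance ratio), and nothing in the text makes that combination likely.

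**What to change.** In section IV.F, Aim 2, replace Student t-tests with Welch (unequal-variance) t-tests, with the corresponding 95% confidence intervals, for weight change and for the lifestyle outcomes. No preliminary variance test is needed.

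The cost is a change of wording before analysis, with no effect on conduct or burden, and at most about 1 percentage point of power in the scenarios checked if the variances are in fact equal. The change does not correct bias from selective dropout; that needs its own missing-data rule, which the plan lacks.

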**Protocol #: 16-1932**

**Project Title: Helping moms to be healthy after baby**

**Principal Investigator: [name] [name]**

**Version Date: 09/08/2017**

**Hypotheses and Specific Aims:**

This protocol outlines details for both a main study and a Substudy.

Main study hypotheses:

1. The multicomponent novel weight loss intervention delivered in WIC will be feasible and acceptable.
2. This intervention will be associated with a greater weight change over 12 weeks compared to control.

Main study aims:

**Aim 1:** To evaluate the feasibility and acceptability of a multi-component novel weight loss intervention delivered in a WIC setting to a population of low-income, predominantly racial/ethnic minority, obese, postpartum women.

**Aim 2:** To evaluate differences in weight change between intervention and control participants to determine preliminary intervention efficacy over a 12-week period.

SUBstudy hypotheses:

1. The multicomponent novel weight loss intervention delivered in WIC will be acceptable.
2. This intervention will be associated with differences in diet, physical activity, and self-efficacy compared to control

SUBstudy aims:

**Aim 1:** To evaluate the acceptability of a multi-component novel weight loss intervention delivered in a WIC setting to a population of low-income, predominantly racial/ethnic minority, obese, postpartum women.

**Aim 2:** To evaluate differences in diet, physical activity, and self-efficacy, between intervention and control participants to determine preliminary intervention efficacy over a 12-week period.

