##### **Secondary:**

- Change in weight over 12 week period

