##### **Secondary:**

- Dietary saturated fat, trans fat, total sugars, "added sugars", fruit and fruit juice, vegetable intake, glycemic load and glycemic index
- Physical activity
- Self-efficacy related to diet and exercise
- Readiness to change
- Eating stimulus index

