**G. Summarize Knowledge to be Gained:** We will learn whether the proposed intervention is feasible and acceptable, which will inform future efforts to design weight loss interventions in WIC settings. If it is feasible and acceptable, then this will support the need to evaluate this intervention on a larger scale. Findings from Aim 2 will help us to understand whether the intervention has an impact on lifestyle changes and weight. Again, this is important for understanding whether we should evaluate this intervention on a larger scale, and will inform sample size estimates for future work.

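### Do unadjusted 0.05 tests on weight and a loosely named set of lifestyle habits undermine the Aim 2 conclusions?

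*Combined protocol and SAP*

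**What the plan says.** The Aim 2 entry in section IV.F opens with its purpose: "To evaluate differences in diet, physical activity, self-efficacy, eating stimulus, and weight change between intervention and control participants to determine preliminary intervention efficacy". The inferential plan beneath it is a single sentence: Student t-tests to "test for differences between intervention and control groups in change in weight (baseline to 12 wks) and in lifestyle habits", at a two-tailed alpha of 0.05. The planned size is 40 (20 per arm), chosen for Aim 1, with enrolment allowed up to 80.

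The outcomes appear in three places:

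- **Hypotheses and Specific Aims, substudy Aim 2:** "To evaluate differences in diet, physical activity, and self-efficacy, between intervention and control participants to determine preliminary intervention efficacy".
- **Section IV.F, Aim 2:** the same three domains plus eating stimulus, with weight brought into the same sentence.
- **Section IV.A, secondary outcomes:** for the main study, one item, "Change in weight over 12 week period". For the substudy, eight dietary measures (saturated fat, trans fat, total sugars, added sugars, then "fruit and fruit juice, vegetable intake, glycemic load and glycemic index"), physical activity, self-efficacy for diet and exercise, readiness to change, and the eating stimulus index.

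Section IV.G describes the use of the results. On feasibility: "If it is feasible and acceptable, then this will support the need to evaluate this intervention on a larger scale". On efficacy: "Findings from Aim 2 will help us to understand whether the intervention has an impact on lifestyle changes and weight". It adds that this bears on whether to run a larger evaluation and "will inform sample size estimates for future work".

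**The concern.** Three features together look troublesome. First, the term lifestyle habits is not mapped to named variables, and the three lists disagree: eating stimulus is missing from the substudy aim, and readiness to change appears only among the outcomes. Second, every test uses 0.05, with no lead substudy outcome, no adjustment and no planned interval. Third, section IV.G intends to learn from Aim 2 about impact, scale-up and future sample size, and no sentence says how an isolated significant result will be read.

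The stake would be a single chance finding, perhaps one of eight dietary outputs, reported as evidence that the intervention changes behaviour. If that outcome were then used to size the next trial, its estimate would tend to be too large, because in a small trial only large observed differences reach significance.

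**Working it through.** The plan states no effect size, SD, power or dropout, so its sample size of 40 cannot be reproduced. The error rates and the precision can be checked.

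**Count of substudy tests** (weight set aside, because it has its own hypothesis and its own outcome list in the main study)

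- Narrow count: 8 dietary measures + 1 activity measure = 9.
- Adding self-efficacy (1 score, or 2 if diet and exercise are scored separately) and eating stimulus: 11 to 12.
- Adding readiness to change: 12 to 13.
- One test for each non-weight domain named in section IV.F: 4.

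The Perceived Stress Scale is collected at baseline only, so it gives no change to test.

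**Chance of at least one p<0.05 with no true effect, independent outcomes:** 1 − 0.95^k

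- k = 4: 1 − 0.8145 = 18.5%
- k = 9: 37.0%
- k = 13: 48.7%

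The expected number of false positives is 0.05k: 0.45 for 9 tests and 0.65 for 13.

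**With correlation.** The documents give no correlations, so these values are assumed. They come from simulated two-sample t-tests at 20 per arm with 60,000 replicates; a fresh run agreed to within 1 percentage point.

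| Assumed correlation | 9 tests, all correlated | 13 tests, all correlated | 9 tests, only the 8 diet outputs correlated | 13 tests, only the 8 diet outputs correlated |
|---|---|---|---|---|
| 0.3 | 33% | 42% | – | – |
| 0.5 | 27% | 34% | 29% | 42% |
| 0.7 | 21% | 25% | 24% | 38% |
| 0.9 | 13% | 14% | 17% | 32% |

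Eight outputs of one dietary screener are unlikely to be independent, so the independent figures probably overstate the risk.

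**Precision at 20 per arm.** The 95% half-width for a mean difference is t(0.975, 38) × √(2/20) = 2.024 × 0.316 = 0.64 SD. This is also the smallest observed difference that reaches p<0.05.

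**Future sample size if a just-significant estimate were taken at face value** (80% power, two-sided 0.05): n per arm = 2(1.960 + 0.842)²/d²

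- d = 0.64: 39
- d = 0.5: 63
- d = 0.3: 175

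These effect sizes are illustrations. The only one tied to this design is 0.64, the significance threshold.

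**Cost of a formal adjustment.** Bonferroni over 13 tests gives 0.05/13 = 0.0038 per test. At 20 per arm, the difference detectable with 80% power rises from 0.91 SD to 1.25 SD. That is a poor exchange in a feasibility pilot.

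**What the documents already settle**

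- *Status of the tests.* The aims and section IV.F both limit Aim 2 to preliminary efficacy. Section IV.A makes feasibility and acceptability primary and all these comparisons secondary. Section IV.C calls the trial a pilot.
- *Reading of non-significant results.* Sections IV.E and IV.F warn that power may be too low to detect differences.
- *Lead efficacy outcome.* Weight is the only efficacy hypothesis and the only secondary outcome of the main study. One test at 0.05 keeps its 5% error whatever happens in the substudy.
- *Which variables.* The purpose statement directly above the t-test sentence names the domains. Section IV.A itemises the substudy outcomes, and the data-collection table gives the instruments and visits.
- *Intervals.* The t-test for a difference in mean change already yields the mean difference, its standard error and its 95% interval.

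**The case for a change.** The strongest case for a change is that the power caveats concern missed effects, while none concerns chance positives across many tests. The plan sets a threshold for statistical significance, and t-tests at that threshold are the only between-group analysis it describes. Significance is therefore the only stated rule for reading the Aim 2 findings that section IV.G relies on. A few sentences would cost nothing: list the variables, report every difference with its interval, and say that the substudy p-values are unadjusted.

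Part of this stands. The lists do differ, the term lifestyle habits is not mapped to them, and no section mentions multiplicity or confidence intervals. A strict reader could even ask whether self-efficacy counts as a habit, although the purpose statement above the test sentence names it.

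The rest does not carry through to the conclusions. Section IV.G speaks of findings, which include estimates and SDs, and those are what sample size planning needs. It puts feasibility and acceptability first. The under-sized future trial requires the investigators to pick out a chance-significant lifestyle outcome and power on its face value, and no section plans that step. The suggested sentences would also leave every test and every p-value as they are.

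**Conclusion.** No change to the plan is needed. The gap is real but small, and a competent analyst fills it from the documents: test the substudy outcomes listed in section IV.A, report each mean difference with its interval and SD, and describe the p-values as unadjusted results from a pilot.

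With no true effect, the chance of at least one nominally significant substudy outcome is about 13% to 49% for 9 to 13 tests, depending on the assumed correlation. For four domain-level tests it is 18.5% if they are independent, and less if they are positively correlated. These figures assume 20 per arm; the correlations are assumptions and not bounds. That chance is tolerable for secondary outcomes labelled preliminary in a 40-person feasibility trial whose size was set for Aim 1, and the weight comparison is unaffected. This judgement assumes that the report keeps the preliminary status stated in the aims and covers all the listed outcomes, as the plan implies.
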